3.4 Patients Disposition and Evaluability

3.4.1 Patient Disposition

A disposition of all enrolled subjects will be provided. This will include the number and percentage of patients evaluated for each of the analysis populations (Section 3.2). The number of patients discontinuing from the study and the primary reason for discontinuation will also be summarized.

3.4.2 Protocol Deviations

A listing of protocol deviations will be presented.

3.5 Demographics and Baseline Characteristics

3.5.1 Demographics

Patient demographics and baseline characteristics will be summarized for the Safety, Efficacy Evaluable, Per Protocol, and Pharmacodynamic Populations.

Descriptive statistics will be provided for age, height, weight, and body mass index (BMI, calculated as weight in kilograms divided by height in meters squared). Frequencies and percentages will be tabulated for sex, race, and ethnicity.

Age will be calculated as (informed consent date – date of birth + 1)/365.25, truncated and displayed as years. BMI will be calculated as weight (kg)/height² (m²), using the weight and height measurements obtained at screening.

3.5.2 Medical History

Medical history will be collected and summarized.

3.5.3 PNH Disease History

The following PNH disease history data will be summarized:

- Age at initial diagnosis (years)
Age at initial diagnosis will be calculated as (date of initial PNH diagnosis – date of birth + 1)/365.25,
- PNH clone size at diagnosis (% RBC, % WBC)
- Complement C5 gene mutation (Present, Absent, unknown)
- Thrombotic event within 6 months prior to screening (yes, no)
- Blood Transfusion within 6 months prior to screening (yes, no).

3.5.4 PNH Treatment History

The following PNH treatment history data will be summarized:

- Eculizumab treatment history
 - Age at initial eculizumab treatment
Age at initial eculizumab treatment will be calculated as (date of initial eculizumab treatment – date of birth + 1)/365.25,
Note: For if the day and month are missing impute July 2nd, if only the day is missing impute the 15th.
 - Duration of eculizumab treatment (months)
Calculated as:
(stop date of eculizumab treatment – of eculizumab treatment+ 1)
/(365.25/12)
Note: For stop date and start date, if the day and month are missing impute July 2nd, if only the day is missing impute the 15th. If corresponding duration calculation yields a negative number, impute a value of 1 day = 1/30.4375 months.
 - Eculizumab dose, units and frequency will be provided in the listings.

3.6 Prior and Concomitant Medications

Incidence of prior and concomitant medication will be presented by therapeutic area, and preferred (generic) drug name.

Prior medications are those that started and stopped before exposure to study medication; concomitant medications are all medications taken during the study period, including those started before but on going at first dose. Where a medication start date is partially or fully missing, and it is unclear as to whether the medication is prior or concomitant, it will be assumed that it is concomitant.

3.7 Exposure to Study Treatment

Prefilled syringes containing RA101495 will be dispensed every 2 weeks. Subjects will also receive a secure container to dispose of used syringes at each visit and should return the used container containing all used syringes. All study drug (syringes) and disposal containers must be returned to the site at the last study visit. Dosing on study visit days will be held until the completion of the PK and PD sample blood collection has been completed.

Treatment duration (number of days patient received study medication) will be described using summary statistics. Treatment duration will be calculated as the Date of last dose – Date of first dose +1.

The number of patients who had a dose escalation and the number of days from baseline where the dose escalation occurred (Date of dose escalation – date of first dose +1) will be summarized.

These analyses will be performed for the Safety Population.

3.8 Safety Analysis

Safety analysis results will be presented using the Safety Population.

3.8.1 Adverse Events

All adverse events will be coded using the Medical Dictionary of Regulatory Activities (MedDRA) Version 18.0 or higher and will be classified by MedDRA system organ class (SOC) and preferred term (PT). Analyses of adverse events will be performed using the safety population.

Treatment emergent adverse events (TEAEs) are defined as follows:

- An AE that occurs after treatment start that was not present at the time of treatment start; or
- An AE that increases in severity after treatment start, if the event was present at the time of treatment start.

The following TEAE summaries will be provided:

- Overall summary of Treatment Emergent Adverse Events
- Incidence of Treatment Emergent Adverse Events by System Organ Class and Preferred Term
- Incidence of Treatment Emergent Adverse Events by System Organ Class, Preferred Term, and Maximum Severity
- Incidence of Treatment Emergent Adverse Events by System Organ Class, Preferred Term, and Relationship to Study Drug
- Incidence of Treatment Emergent Adverse Events Leading to Study Discontinuation by System Organ Class and Preferred Term
- Listing of Serious Adverse Events by System Organ Class and Preferred Term.

For these summaries, the number and percentage of patients who experienced at least one of the TEAE as well as the number and percentage of patients who experienced each specific SOC and PT will be presented. The corresponding number of TEAEs will also be presented.

For the presentation of TEAE incidences, the SOCs will be sorted alphabetically, and within SOC, the preferred term (PT) will be used and presented by decreasing total frequency.

3.8.1.1 Determining Treatment Emergent with Adverse Event Dates

The following rules apply when determining if an AE is treatment-emergent in the scenario where the start date is missing or partially missing. These rules provide an algorithm to “impute” a complete AE start date which will then be used to determine if the AE is treatment emergent.

AE start date missing day and month:

- If the year is the same as the year of the treatment start date, the day and month of the date of treatment start date will be assigned to the missing fields.
- If the year is prior to the year of the treatment start date, December 31 will be assigned to the missing fields.
- If the year is after the year of the date of the treatment start date, January 1 will be assigned to the missing fields.

AE start date missing month only:

- The day will be treated as missing, and both month and day will be replaced according to the above procedure.

AE start date missing day only:

- If the month and year are the same as the month and year of the treatment start date, the day of the treatment start date will be assigned to the missing day.
- If either the year is before the year of the date of the treatment start date or if both years are the same but the month is before the month of the treatment start date, the last day of the month will be assigned to the missing day.
- If either the year is after the year of the treatment start date or if both years are the same but the month is after the month of the treatment start date, the first day of the month will be assigned to the missing day.

AE start date completely missing:

- If the AE end date is complete and after the treatment start date, the treatment start date will be assigned to the missing start date.
- If the end date is complete and before the treatment start date, the end date will be assigned to the missing start date
- Otherwise the AE start date will be assigned the treatment start date.

If the end date is complete and the imputed start date as above is after the end date, the start date will be imputed by the end date.

3.8.2 Adverse Events of Special Interest

3.8.2.1 Thrombotic Adverse Events

A separate table for thrombotic AEs will be presented, summarizing TEAEs by PT. The events in Table 6 (MAVE criteria, 2007]) will be evaluated in the assessment of thrombotic AEs.

Table 6: Thrombotic Event Description (MAVE Criteria)

MAVE Criteria	AE Preferred Term Mapping
Thrombophlebitis/Deep vein thrombosis	Preferred Term: 10051055 Deep vein thrombosis Preferred Term: 10043570 Thrombophlebitis
Pulmonary embolus	Preferred Term: 10037377 Pulmonary embolism
Myocardial infarction	Preferred Term: 10028596 Myocardial infarction
Transient ischemic attack	Preferred Term: 10044390 Transient ischaemic attack
Renal vein thrombosis	Preferred Term: 10038548 Renal vein thrombosis
Acute peripheral vascular occlusion	Preferred Term: 10053648 Vascular occlusion
Amputation (non-traumatic, non-diabetic)	Preferred Term: 10061627 Amputation
Mesenteric/Visceral vein thrombosis	Preferred Term: 10027402 Mesenteric vein thrombosis Preferred Term: 10077829 Visceral venous thrombosis
Unstable angina	Preferred Term: 10002388 Angina unstable
Mesenteric/Visceral arterial thrombosis	Preferred Term: 10027397 Mesenteric artery thrombosis Lower level term: 10043611 Thrombosis arterial
Hepatic/Portal vein thrombosis	Preferred Term: 10019713 Hepatic vein thrombosis Preferred Term: 10036206 Portal vein thrombosis
Dermal thrombosis	Lower level term: 10042545 Superficial phlebothrombosis
Gangrene (non-traumatic, non-diabetic)	Preferred Term: 10017711 Gangrene Preferred Term: 10009971 Colon gangrene Preferred Term: 10017954 Gastrointestinal gangrene
Cerebral arterial occlusion/cerebrovascular accident	Preferred Term: 10008190 Cerebrovascular accident Preferred Term: 10008089 Cerebral artery occlusion
Cerebral venous occlusion	Preferred Term: 10076895 Cerebral vascular occlusion
Renal arterial thrombosis	Preferred Term: 10038380 Renal artery thrombosis

Abbreviation: MAVE=major adverse vascular event.

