12.1.3 ADVERSE EVENTS OF SPECIAL INTEREST

12.1.3.1 THROMBOTIC ADVERSE EVENTS

All subjects should be monitored for signs and symptoms of thrombotic events at all study visits (weekly for the first 4 weeks followed by every 2 weeks). The method of diagnosis (e.g. ultrasound, computed tomography [CT], magnetic resonance imaging [MRI], venogram, or other [specify]) for any reported event should be recorded in the eCRF. All AEs should be recorded as AEs per [Section 12.1](#) and [Section 12.3](#).

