13.3.4.2 ADVERSE EVENTS OF SPECIAL INTEREST

13.3.4.2.1 THROMBOTIC ADVERSE EVENTS

Thrombotic AEs will be summarized separately by system organ class, and preferred term. The events in [Table 6](#) (MAVE criteria [[Hillmen, 2007](#)]) will be evaluated in the assessment of thrombotic AEs:

Table 6 Thrombotic Event Description (MAVE Criteria)

Thrombophlebitis/Deep vein thrombosis	Mesenteric/Visceral arterial thrombosis
Pulmonary embolus	Hepatic/Portal vein thrombosis
Myocardial infarction	Dermal thrombosis
Transient ischemic attack	Gangrene (non-traumatic, non-diabetic)
Renal vein thrombosis	Cerebral arterial occlusion/cerebrovascular accident
Acute peripheral vascular occlusion	Cerebral venous occlusion
Amputation (non-traumatic, non-diabetic)	Renal arterial thrombosis
Mesenteric/Visceral vein thrombosis	Other
Unstable angina	

Abbreviation: MAVE=major adverse vascular event.

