2.2.3.6 Blood Chemistry and Hematology

Clinical chemistry and hematology analytes to be collected are identified in Table 1 and should be performed as specified in the Time and Events (Table 2).

Table 1: Clinical Chemistry, Hematology, and Coagulation Analytes

Clinical Chemistry	Hematology
alanine aminotransferase (ALT)	free hemoglobin
albumin	haptoglobin
alkaline phosphatase (ALP)	hematocrit
amylase	hemoglobin
aspartate aminotransferase (AST)	mean corpuscular hemoglobin (MCH)
bicarbonate	mean corpuscular hemoglobin concentration (MCHC)
bile acids	mean corpuscular volume (MCV)
bilirubin (total, direct, and indirect)	platelet count
blood urea nitrogen (BUN)	RBC count
calcium	reticulocyte count
chloride	white blood cell (WBC) count and differential (%)
creatinine	
gamma-glutamyl transferase (GGT)	Coagulation
glucose	international normalized ratio (INR)/prothrombin time (PT)
lactate dehydrogenase (LDH)	fibrinogen
lipase	fibrinogen
potassium	
sodium	Other
total protein	C-reactive protein (CRP)
uric acid	creatine phosphokinase (CPK)

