3.8.3 Clinical Laboratory Evaluation

A list of the clinical chemistry, hematology, and coagulation analytes are listed in Table 1.

Quantitative laboratory endpoints will be summarized by time point using descriptive statistics.

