3.8.3.1 Hepatic Laboratory Tests: NCI CTCAE Grading

The liver functions test to be summarized via the National Cancer Institute (NCI) Common Terminology Criteria for Adverse Events (CTCAE) criteria are provided in Table 7.

Table 7: CTCAE Grading Criteria for Selected Liver Function Tests

Lab Test	Grade/Criteria			
	1	2	3	4
alanine (ALT)	> 1.0 - 3.0 (x ULN)	>3.0 - 5.0 (x ULN)	>5.0 - 20.0 (x ULN)	> 20.0 (x ULN)
alkaline phosphatase (ALP)	>1.0 - 2.5 (x ULN)	>2.5 - 5.0 (x ULN)	>5.0 - 20.0 (x ULN)	> 20.0 (x ULN)
direct bilirubin	> 1.0 – 1.5 (x ULN)	>1.5 – 3.0 (x ULN)	>3.0 - 10.0 (x ULN)	> 10.0 (x ULN)
gamma-glutamyl transferase (GGT)	>1.0 - 2.5 (x ULN)	>2.5 - 5.0 (x ULN)	>5.0 - 20.0 (x ULN)	>20.0 (x ULN)

Grading criteria based on Common Terminology Criteria for Adverse Events (CTCAE) v4.03

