14.2.12.3*	Subject Plots of RA103488 Concentrations Over Time by Cohort, Linear Scale, PK Population
14.2.12.4*	Subject Plots of Plasma RA103488 Concentrations Over Time by Cohort, Log Scale, PK Population
14.2.13.1	Mean Plasma RA102758 Concentrations Over Time by Cohort, Linear Scale, PK Population
14.2.13.2	Mean Plasma RA102758 Concentrations Over Time by Cohort, Log Scale, PK Population
14.2.13.3*	Subject Plots of RA102758 Concentrations Over Time by Cohort, Linear Scale, PK Population
14.2.13.4*	Subject Plots of RA102758 Concentrations Over Time by Cohort, Log Scale, PK Population
14.2.14.1	Mean Plasma Eculizumab Concentrations Over Time for Cohort B, Linear Scale, PK Population
14.2.14.2	Mean Plasma Eculizumab Concentrations Over Time for Cohort B, Log Scale; PK Population

Listing Number	Listing Title
16.2.1.1	Patient Disposition; Safety Population
16.2.1.2	Patient Screening and Enrollment; All Screened Patients
16.2.2.1	Medical History; Safety Population
16.2.2.2	PNH Disease History; Safety Population
16.2.2.3	PNH Disease History: Thrombotic Events; Safety Population
16.2.2.4	PNH Treatment History; Safety Population
16.2.2.5	Transfusion History; Safety Population
16.2.2.6	LDH History; Safety Population
16.2.2.7	Neisseria meningitidis Testing; Safety Population
16.2.2.8	Pregnancy Testing; Safety Population
16.2.3.1	Prior Medications; Safety Population
16.2.3.2	Concomitant Medications; Safety Population
16.2.4.1	Study Drug Administration: In Clinic; Safety Population
16.2.4.2	Study Drug Dispensation; Safety Population
16.2.5	Demographics; Safety Population
16.2.6	Efficacy Assessments; Safety Population
16.2.7	Pharmacodynamic Endpoints

Listing Number	Listing Title
16.2.8.1	Plasma Pharmacokinetic Sample Collection Times and RA101495 and Metabolites Concentrations
16.2.8.2	Individual Plasma RA101495 PK Parameters
16.2.8.3	Plasma Pharmacokinetic Sample Collection Times and Eculizumab Concentrations
16.2.9.1	EORTC QLQ-C30: Items; Safety Population
16.2.9.2	EORTC QLQ-C30: Scales; Safety Population
16.2.9.3	FACIT-Fatigue; Safety Population
16.2.9.4	EQ-5D; Safety Population
16.2.9.5	Treatment Satisfaction; Safety Population
16.2.10.1	Adverse Events; Safety Population
16.2.10.2	Adverse Events: Treatment Required; Safety Population
16.2.10.3	Adverse Events: MedDRA Coding; Safety Population
16.2.10.4	Deaths; Safety Population
16.2.10.5	Thrombotic Adverse Events; Safety Population
16.2.11	Injection Site Reactions; Safety Population

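### Minor reporting gaps in the supplied SAP: the thrombotic term map drops the protocol's Other category, and the post-lock output list names no anti-drug antibody output

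*SAP*

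**What the plan says.** **Thrombotic events.** Protocol 13.3.4.2.1 says "Thrombotic AEs will be summarized separately by system organ class, and preferred term" and points to its Table 6, a list of MAVE categories that includes Other. SAP 3.8.2.1 says "The events in Table 6 (MAVE criteria, 2007]) will be evaluated in the assessment of thrombotic AEs". The SAP's Table 6 sets coded terms against each category and has no Other row. The dedicated output is Table 14.3.1.4. The post-lock list adds listing 16.2.10.5, "Thrombotic Adverse Events; Safety Population", without a selection rule.

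**ADA.** Protocol 7.2.1 and SAP 3.3.1 make ADA part of the safety evaluation. SAP 3.8.4 plans the count and share of confirmed-positive patients at each scheduled time, and the SAP body lists this as Table 14.3.2.7. In the post-lock list, 14.3.2.7 is a urinalysis table. Protocol 11.2.9 also promises comparisons for subjects with confirmed ADA and for those with neutralizing ADA. It leaves the PK, PD, safety and efficacy content to the SAP.

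**Liver tests.** Protocol 12.1.3.2 names six: ALP, ALT, AST, GGT, direct bilirubin and indirect bilirubin. Protocol 13.3.4.2.2 says liver tests will be CTCAE-graded. SAP Table 7, as supplied, grades ALT, ALP, direct bilirubin and GGT.

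**The concern.** Thrombosis is an adverse event of special interest here, and Other is the only protocol category that can hold a thrombosis that none of the named categories describes. With that row gone and no rule for unmapped terms, a programmer who follows the map would leave such an event out of the thrombotic table. The thrombotic table and the overall table could then disagree with nothing in the plan to explain it. In a study of 6–8 subjects, one event can change the whole table.

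ADA results are scheduled for every subject, yet the latest output list supplied has no named place for them. The protocol hands the definition of the ADA subset analyses to the SAP, and the supplied SAP does not define them.

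If AST is truly absent from Table 7, it would be reported without the grading that the protocol promises.

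**Working it through.** The plan gives no figure of its own on this point. The check compares lists across the documents.

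**1. Which SAP text is in hand.** The post-lock document says that it builds on SAP version 3.0 of 22 March 2018. It describes Tables 14.2.11.1 to 14.2.11.3 as plasma and metabolite concentration tables. In the supplied body, 14.2.11.2 is eculizumab and 14.2.11.3 is PK parameters. The body also cites protocol version 1.1 of 20 October 2016, while the supplied protocol is Amendment 1 of 17 January 2017. The supplied body is therefore not version 3.0.

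**2. Thrombotic map.**

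| | Protocol Table 6 | SAP Table 6 |
|---|---|---|
| Categories | 17 | 16 |
| In one list only | Other | none |
| Coded terms | none given | 23 (21 preferred, 2 lower level) |

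The difference is 17 − 16 = 1, and that one is Other. The two lower-level entries are arterial thrombosis and superficial phlebothrombosis. SAP 3.8.2.1 builds the table by preferred term, which is a further reason to state how events are selected.

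**3. Where an unmapped event would still appear.** SAP 3.8.1 keeps "Incidence of Treatment Emergent Adverse Events by System Organ Class and Preferred Term", and listing 16.2.10.1 covers adverse events. Only the dedicated table is at risk. Listing 16.2.10.5 may or may not be, since its rule is not given.

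**4. ADA in the output lists.** The supplied body list has 77 tables, one of which is ADA. The post-lock list has 85 tables + 45 figures + 40 listings = 170 titles, and none names ADA. The post-lock document marks with an asterisk the tables and figures it creates or changes. The urinalysis entry at 14.3.2.7 has no asterisk. The CH50 table has also gone, and four total bilirubin tables have appeared, again unstarred. This pattern fits a change made in a revision between the supplied body and the post-lock document, probably version 3.0.

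ADA sampling is on Days 1, 29, 57 and 84. That gives 4 × 6 = 24 to 4 × 8 = 32 scheduled results, of which 3 × 6 = 18 to 3 × 8 = 24 are post-baseline.

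**5. ADA subset analyses.** Protocol 11.2.9 describes screening, confirmatory, titre and neutralizing tiers, and comparisons by confirmed and by neutralizing status. SAP 2.2.3.10 mentions only a validated assay, and 3.8.4 only confirmed positives. No subset analysis is defined.

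**6. Liver tests.** Six protocol tests minus the four in SAP Table 7 leaves AST and indirect bilirubin. AST is in SAP Table 1, so SAP 3.8.3 covers it: "Quantitative laboratory endpoints will be summarized by time point using descriptive statistics". It is also covered by clinical chemistry listing 16.2.12.2.

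**The case against.** The strongest reply is that this compares documents from different stages. The body was written against protocol version 1.1, is set here against Amendment 1, and is then read with a list based on version 3.0. The post-lock figure titles even refer to cohorts, which the supplied single-arm SAP does not define. This stands: neither the missing Other row, nor the missing AST row, nor the undefined ADA subsets can be attributed to version 3.0. The ADA list gap is less exposed, because the post-lock list is the latest one supplied and the protocol makes ADA a safety evaluation.

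On AST, the table may have been damaged when the PDF was read. The ALT label in Table 7 is cut short. SAP Table 1 prints fibrinogen twice and lacks the PTT/aPTT row that protocol Table 4 has. This also stands, and the AST point is conditional for that reason.

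On Other, the protocol does not define it, and SAP 3.8.2.1 does not say that only mapped terms count. That limits the point to a missing rule, but the rule is still missing.

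Three stronger readings are tempting and not supported:
- *Thrombotic events would vanish from the report.* They would not; the general tables and listings still carry them.
- *AST goes unanalysed, or every scheduled AST value loses a grade.* AST is summarised and listed, and Table 7 grades only values above the ULN.
- *The sponsor dropped the ADA analysis after lock.* A missing title does not show this. SAP 3.8.4 still commits to the summary, SAP 3.1.2 promises listings of all clinical data, and the post-lock text withdraws neither. The listing index in the supplied body breaks off, so whether it named an ADA listing cannot be seen.

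**Conclusion.** The point holds as a minor safety-reporting correction, limited to the supplied SAP text.

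- **Thrombotic map:** 16 of 17 categories are mapped. One unmapped thrombosis could be left out of Table 14.3.1.4.
- **ADA:** the plan's text and the post-lock list conflict. None of 170 titles covers 24–32 scheduled results, and the protocol 11.2.9 subset analyses are undefined.
- **AST:** a gap only if the source PDF shows no AST row.

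There is no effect on the primary endpoint or on data collection. The conclusion assumes that version 3.0 has not already closed these gaps, which cannot be seen from the documents supplied.

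**What to change.** First check each item in SAP version 3.0, and check Table 7 in the source PDF. Where a gap persists:

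1. **Thrombotic events.** Restore an Other row in SAP Table 6, filled by documented medical review of treatment-emergent terms not mapped to a named category. Apply the same rule to Table 14.3.1.4 and listing 16.2.10.5. The named categories can stay. Protocol 12.1.3.1 says the method of diagnosis "for any reported event should be recorded in the eCRF", so the review has material to work from.
2. **ADA.** Restore the summary table and add a by-subject listing with confirmed and neutralizing status. For the protocol 11.2.9 subsets, either show PK, PD, LDH and adverse events by subject for any ADA-positive subject, or state that these analyses are dropped and why.
3. **Liver tests, only if the AST row is truly absent.** Add AST to the CTCAE grading, and either add indirect bilirubin or state why it is not graded.

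The cost is a version check, a short review of coded terms, one ADA table and one listing, and perhaps one or two laboratory rows, for at most 8 subjects and from data already scheduled. The downside is that filling Other takes medical judgement in an open-label study. Anything done after lock is post hoc and should be labelled so.
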